- o Specific ocular tests will include assessment of ocular/visual symptoms and ocular exams including visual acuity, slit lamp under dilatation, and Schirmer's test at screening and whenever clinically indicated.
- p AE: For participant who was prescreened and had fresh biopsy, only the Adverse Events related to the fresh biopsy procedure itself should also be reported in eCRF as general requirement of AE/SAE with the reporting time frame interval of 1 month for the prescreening period after fresh biopsy.
- q Concomitant medication will be recorded in the eCRF from 28 days prior to the first study intervention administration, before every cycle during the study treatment period, and for up to 30 days after the final dose of study intervention. Once the participant has withdrawn from study treatment, concomitant medication should only be recorded if used to treat new or unresolved study treatment-related adverse events.
- r Tumor assessment will be made at every 8 weeks interval (± 7 days window) during the study treatment period until radiological disease progression; initiation of further anti-cancer therapy; death; or study cut-off of the secondary ORR endpoint of the triplet cohort. The scheduled tumor assessment time point will not be modified in case of a cycle delay.
- s CEA samples should be collected before IMP infusion.

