- q Concomitant medication will be recorded in the eCRF from 28 days prior to the first study intervention administration, before every cycle during the study treatment period, and for up to 30 days after the final dose of study intervention. Once the participant has withdrawn from study treatment, concomitant medication should only be recorded if used to treat new or unresolved study treatment-related adverse events.
- r Tumor assessment will be made at every 6 weeks interval (± 7 days window) during the study treatment period until radiological disease progression; initiation of further anti-cancer therapy; death; or study cut-off of the secondary ORR endpoint of the triplet cohort. The scheduled tumor assessment time point will not be modified in case of a cycle delay.
- s CEA samples should be collected before IMP infusion.

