The study cut-off for the secondary ORR endpoint analysis of triplet cohort corresponds to the date on which all evaluable treated patients have had at least 2 post baseline tumor assessments, experienced confirmed objective response, or have discontinued the study for any reason. This study cut-off will occur approximately 4.5 months after the date of the first IMP administration of the last participant: 3 months for 2 tumor assessments and 1.5 months if a confirmation of response is needed.

After the study cut-off dates for the primary ORR analysis of doublet cohort and for the secondary ORR analysis of triplet cohort, patients who are still receiving study treatment can continue study treatment, if clinical benefit is observed, until PD, unacceptable toxicity, or withdrawal of participant's consent, and will continue to undergo all assessments as per the study flow chart.

The expected duration of study intervention for participants may vary, based on progression date; median expected duration of study per participant is estimated as 11 months (up to 1 month for screening, a median of 6 months for treatment, and a median of 4 months for end-of-treatment assessments and safety follow-up visit).

Study Team will add details on the specific changes to follow-up for patients with ongoing treatment after final study cut-off date.

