8.1 EFFICACY ASSESSMENTS

The assessment of antitumor activity of tusamitamab ravtansine combined with ramucirumab in doublet cohort is the primary efficacy objective.

All participants treated must have at least one measurable lesion as per RECIST v1.1 for inclusion based on tumor assessment defined in the SOA, [Section 1.3](#).

For the doublet cohort: Tumor assessment will be made every 8 weeks (± 7 days window), and a scheduled assessment time point will not be modified in case of a cycle delay. Thoracic-abdominal-pelvic CT-scan or MRI and any other examinations as clinically indicated will be performed to assess disease status at baseline; then every 8 weeks during the study treatment period until radiological disease progression, initiation of further anticancer therapy, death, or study cut-off of the secondary ORR endpoint of the triplet cohort, whichever comes first; and at the end of study treatment, except if already done at last cycle. Confirmatory radiological evaluation will be performed at least 4 weeks after initial documentation of response. After IMP discontinuation, tumor assessment should be performed at EOT for patients without imaging performed within past 4 weeks, and every 12 weeks (± 7 days) after the last tumor assessment until

disease progression or initiation of a new anticancer treatment, death, or the study cut-off date of the secondary ORR endpoint of the triplet cohort, whichever comes first.

For the triplet cohort: Tumor assessment will be made every 6 weeks (± 7 days window), and a scheduled assessment time point will not be modified in case of a cycle delay.

Thoracic-abdominal-pelvic CT-scan or MRI and any other examinations as clinically indicated will be performed to assess disease status at baseline; then every 6 weeks during the study treatment period until IMP discontinuation; and at the end of study treatment, except if already done at last cycle. Confirmatory radiological evaluation will be performed at least 4 weeks after initial documentation of response. After IMP discontinuation, tumor assessment should be performed at EOT for patients without imaging performed within past 4 weeks.

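### For participants still on drug after the triplet ORR cut-off, the protocol gives conflicting rules in both cohorts on whether interval scans continue

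*Protocol*

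**What the plan says.** **Rules that stop interval scans at the triplet ORR cut-off.** Footnote r of 1.3.2 (triplet, 6-weekly) lists radiological progression and then "initiation of further anti-cancer therapy; death; or study cut-off of the secondary ORR endpoint of the triplet cohort". Footnote r of 1.3.1 (doublet, 8-weekly) ends with the same item, "or study cut-off of the secondary ORR endpoint of the triplet cohort". Both footnotes govern scans during study treatment. The doublet on-treatment sentence of 8.1 agrees: "death, or study cut-off of the secondary ORR endpoint of the triplet cohort, whichever comes first; and at the end of study treatment".

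**Rules that keep scans or dosing going.** Section 7 says that after the doublet and triplet ORR cut-offs, participants still on treatment "can continue study treatment, if clinical benefit is observed, until PD, unacceptable toxicity" or withdrawal of consent, and "will continue to undergo all assessments as per the study flow chart". Section 4.1 says the same for the doublet after its own ORR cut-off. It also gives the doublet tumor assessments every 8 weeks during the treatment period, with no end date. For the triplet, 8.1 schedules scans "then every 6 weeks during the study treatment period until IMP discontinuation", with no cut-off date.

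**Related text.** Section 7.1.1 lists disease progression among the reasons to stop study intervention. For doublet participants already off drug, a separate sentence of 8.1 ends the 12-weekly follow-up scans at "death, or the study cut-off date of the secondary ORR endpoint of the triplet cohort, whichever comes first". Section 7 also carries an open item: "Study Team will add details on the specific changes to follow-up for patients with ongoing treatment after final study cut-off date".

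**The concern.** Dosing ends at progression, but one set of rules ends the scans that would show progression at an administrative date. Section 7 does not settle this. It refers sites to the flow chart, and the flow chart contains footnote r.

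For anyone on drug after the cut-off, a site following footnote r would learn of radiological progression only from an unscheduled scan, clinical signs or the end-of-treatment scan. The end-of-treatment scan follows the decision to stop, so it cannot prompt that decision. The participant could then receive an antibody-drug conjugate and an antiangiogenic, with or without pembrolizumab, past progression. A site following 4.1 or the triplet paragraph of 8.1 would keep scanning, so practice could differ between sites.

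The statistical question is whether any endpoint depends on the missing scans.

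**Working it through.** **1. Rules side by side, for a participant on drug after the triplet ORR cut-off**

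| Source | Doublet | Triplet |
|---|---|---|
| Footnote r (1.3.1, 1.3.2) | stop | stop |
| 8.1, on-treatment text | stop | continue until drugs stopped |
| 4.1 | every 8 weeks during treatment | no on-treatment scan rule |
| Section 7 | all assessments, per flow chart | all assessments, per flow chart |

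Each cohort has at least one rule that stops the scans and one that continues them.

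**2. The plan's cut-off time.** Two 6-weekly scans plus one more interval for confirmation is 18 weeks, or 18/4.348 = 4.1 months. The protocol rounds 6 weeks to 1.5 months, so 3 + 1.5 = 4.5 months after the last triplet first dose. The stated figure is reproduced.

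**3. Inputs for the size**
- Median time on treatment: 6 months (Protocol, Section 7).
- First participant enrolled: 28-Oct-2020 (SAP, Version history). Amendment 02: 20-Dec-2022. The interval is 25.7 months.
- Doublet treated: up to 36 (Protocol 9.2); SAP 1.1 gives 30 to 36.
- Assumed: exponential time on drug and even entry over A months. A = 12 is borrowed from the study-level enrollment estimate in Protocol 4.1; no figure is given for the doublet alone.
- L = months from the amendment to the last triplet first dose. It is not given, so I vary it. The lower limit comes from the 1-week stagger plus the 21-day DLT window: 28 days = 0.9 months for six participants, with no start-up delay.

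**4. Formula.** P(on drug at t) = 0.5^(t/6). Averaged over times since first dose from a to b, this is (6/ln 2)(0.5^(a/6) − 0.5^(b/6))/(b − a). For the doublet, b = 25.7 + 4.5 + L = 30.2 + L and a = b − A. The value a is also the earliest time after first dose at which the scan gap can open.

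**5. Doublet, out of 36**

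| L | A = 12: a to b | mean | on drug | A = 24: a to b | mean | on drug |
|---|---|---|---|---|---|---|
| 0.9 | 19.1 to 31.1 | 0.059 | 2.1 | 7.1 to 31.1 | 0.149 | 5.3 |
| 6 | 24.2 to 36.2 | 0.033 | 1.2 | 12.2 to 36.2 | 0.082 | 3.0 |
| 12 | 30.2 to 42.2 | 0.016 | 0.6 | 18.2 to 42.2 | 0.041 | 1.5 |
| 18 | 36.2 to 48.2 | 0.008 | 0.3 | 24.2 to 48.2 | 0.021 | 0.7 |

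With 30 treated instead of 36, multiply the counts by 30/36; for example, 1.2 becomes 1.0.

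**6. Triplet.** Times since first dose run from 4.5 to 4.5 + accrual. With 6 months of accrual (assumed) the mean is 0.429, or 2.6 of 6 and 5.1 of 12. With 12 months it is 0.322, or 1.9 of 6 and 3.9 of 12.

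**7. Scans at issue.** A further median of 6 months is 26.1 weeks: 26.1/8 = 3.3 doublet scans or 26.1/6 = 4.3 triplet scans per participant.

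**8. Endpoints.** By its definition, the triplet ORR cut-off comes after each evaluable participant has two post-baseline scans, a confirmed response or has left the study. The doublet ORR has its own cut-off. The triplet has no PFS or DOR endpoint. SAP 4.9 updates all doublet analyses at the end of the study, so late PFS and DOR could be touched. SAP 4.4.2.2.2 reports event-free probabilities at 2 to 12 months. With A = 12 the gap opens at 19.1 months or later, beyond that range. It falls inside the range only if a = 30.2 + L − A is below 12, that is, if A exceeds 18.2 + L.

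**The case against.** The strongest reply is that Section 7 is the only text written for participants treated after the cut-offs, and it keeps all assessments. If footnote r overrides it, those words mean nothing for scans. That shows an intent to keep scanning, and it supports correcting footnote r. It does not remove the conflict, because Section 7 names the flow chart as the schedule.

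Second, other checks remain: the end-of-treatment scan, clinically indicated examinations, and ECOG and physical examination before each infusion. Circulating CEA also has its own interval entry in both flow charts, and footnote r does not govern it. This stands and lowers the risk. However, Appendix 7 does not allow a tumor marker alone to define response, and examinations prompted by symptoms can miss silent progression.

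Third, Section 7 openly defers the details for these participants. That acknowledges the group but gives sites no rule in the current text.

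Fourth, few people are affected, and the triplet had not started when the SAP was written. If no triplet cut-off ever occurs, the clause never applies. This stands, and it is why the point is minor.

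A reader might infer that doublet surveillance is cleanly removed while only the triplet text conflicts. Section 4.1 does not support that: its 8-weekly doublet scans have no cut-off, so both cohorts have conflicting text. A reader might also infer bias in the response rate. The definitions of the two ORR cut-offs do not support that.

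**Conclusion.** The inconsistency is real in both cohorts, minor, and mainly a matter of patient management. Following footnote r leaves no scheduled interval scan for participants whom Section 7 allows to be dosed until progression.

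Under exponential time on drug with a 6-month median and 12-month doublet accrual, about 0.3 to 2 of 36 doublet participants are on drug at the cut-off. For the triplet, 6 to 12 participants over an assumed 6 to 12 months of accrual give about 2 to 5. ORR is essentially unaffected.

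It is tempting to say that doublet PFS at 2 to 12 months cannot change. That holds under 12-month accrual, but the documents give no doublet accrual time or last first-dose date. With 24 months of accrual and the shortest possible triplet run-in, the gap could open about 7 months after first dose, with about 5 participants on drug. Even then, SAP Appendix 3 counts unscheduled scans, and deaths still count as PFS events, subject to the SAP's rule on consecutive missed assessments.

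**What to change.** Delete "or study cut-off of the secondary ORR endpoint of the triplet cohort" from footnote r of 1.3.1, footnote r of 1.3.2 and the on-treatment sentence of the doublet paragraph of 8.1. On-treatment scans then end at radiological progression, new anticancer therapy or death. Keep the clause in the doublet text for participants already off drug: footnote d of 1.3.1, Section 4.1, Section 7 and the last doublet sentence of 8.1.

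Add a sentence to Section 7: *Participants still receiving IMP after the study cut-offs continue tumor assessments every 8 weeks (doublet) or 6 weeks (triplet) until PD or IMP discontinuation.* Add it beside the existing sentence on details from the study team and do not replace that sentence, which also covers follow-up other than scans.

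The cost is one clause deleted in three places and one sentence added, through an amendment with IRB/IEC approval; it can ride on the next one. Participants on drug have a few more routine scans, about 3 (doublet) or 4 (triplet) over a further median of 6 months. At the final PFS and DOR update, doublet participants on drug would keep scheduled scans after the cut-off, while those off drug and progression-free would not. That difference in follow-up should be noted when late estimates are read.

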1.3.3 Pharmacokinetic/Anti-therapeutic Antibody Flow Charts

1.3.3.1 Doublet cohort - Part 1: Safety run-in

Intervention period		C1					C3	C4					C6 + beyond ^{c,d,e}	EOT
Day		D1		D4	D8	D15	D1	D1		D4	D8	D15	D1	D30 ± 5 days after last IMP
Ramucirumab	IV infusion	X—	—X				X	X	X				X	X
	Sample RNT (hours) Ref. ramucirumab SOI	SOI	EOI				336h (SOI)	SOI	SOI					SOI
	Sample time window	(-24h, SOI)	± 10 min				± 48 h	(-24h, SOI)	(-24h, SOI)					(-24h, SOI)
	PK sample ID	S00 ^a	S01				S02 ^{a,b}	S00 ^a	S00 ^a					S00 ^{a,c}
Tusamitamab rfvatsine	IV infusion	X—	—X				X	X	X—	—X			X	X
	Sample RNT (hours) Ref. tusamitamab rfvatsine SOI	SOI	EOI	EOI+4h	72h	168h	336h (SOI)	SOI	SOI	EOI	EOI+4h	72h	168h	336h (SOI)
	Sample time window	(-24h, SOI)	± 10 min	± 30 min	± 5 h	± 24 h	± 48 h	(-24h, SOI)	(-24h, SOI)	± 10 min	± 30 min	± 5 h	± 24 h	± 48 h
	PK sample ID	P00 ^a	P01	P02	P03	P04	P05 ^{a,b}	P00 ^a	P00 ^a	P01	P02	P03	P04	P05 ^{a,b}
ATA sample ID		AB00 ^a					AB01 ^{a,b}	AB00 ^a						AB00 ^{a,e}
														ABF00

Abbreviations: AESI = adverse event of special interest; ATA = Anti-therapeutic Antibody; C = Cycle; D = Day; EOI = End of infusion; EOT = End-of-treatment; IMP = Investigational Medicinal Product; IV = intravenous; P = Plasma; PK = Pharmacokinetics; RNT = Relative nominal time; S = Serum; SOI = start of infusion.

a Samples collected strictly before start of infusion (SOI), tusamitamab rfvatsine and ramucirumab predose samples can be collected at the same time before ramucirumab administration.

b Sample must be collected even if the infusion planned is not done or delayed on C2D1 (corresponding to C1D15) and on C5D1 (corresponding to C4D15).

c Ramucirumab PK samples will be collected at SOI at Cycle 7 only.

d Tusamitamab rfvatsine PK samples will be collected at SOI each cycle at Cycle 6 and Cycle 7 and thereafter at Cycle 13 only.

e Tusamitamab rfvatsine ATA samples will be collected at SOI at Cycle 7 and thereafter every 6 cycles (ie, C7, C13, C19...).

Note: Upon notification from the Sponsor, the sampling time-points for PK and ATA may be reduced during the course of the study, based on new information.

1.3.3.2 Doublet cohort - Part 2

Cycle		C1		C2	C3	C4		C5 + beyond ^{b,c,d}	EOT
Day		D1		D4	D1	D1		D1	D30 ± 5 days after last IMP
Ramucirumab	IV infusion	X—	—X		X	X	X	X	
	Sample RNT (hours) Ref. ramucirumab SOI	SOI	EOI		SOI	SOI	SOI	SOI	
	Sample time window	(-24h, SOI)	± 10 min		(-24h, SOI)	(-24h, SOI)	(-24h, SOI)	(-24h, SOI)	
	PK sample ID	S00 ^a	S01		S00 ^a	S00 ^a	S00 ^a	S00 ^{a,b}	
tusamitamab rfvntansine	IV infusion	X—	—X		X	X	X	X	
	Sample RNT (hours) Ref. tusamitamab rfvntansine SOI	SOI	EOI	72h	SOI	SOI	SOI	EOI+1h	SOI
	Sample time window	(-24h, SOI)	± 10 min	± 24 h	(-24h, SOI)	(-24h, SOI)	(-24h, SOI)	± 10 min	(-24h, SOI)
	PK sample ID	P00 ^a	P01	P02	P00 ^a	P00 ^a	P00 ^a	P01	P00 ^{a,c}
	ATA sample ID	AB00 ^a			AB00 ^a	AB00 ^a		AB00 ^{a,d}	ABF00

Abbreviations: ATA = Anti-therapeutic Antibody; C = Cycle; D = Day; EOI = End of infusion; EOT = End-of-treatment; IMP = Investigational Medicinal Product; IV = intravenous; P = Plasma; PK = Pharmacokinetics; RNT = Relative nominal time; S = Serum; SOI = start of infusion.

a Samples collected strictly before start of infusion (SOI), tusamitamab rfvntansine and ramucirumab predose samples can be collected at the same time before ramucirumab administration.

b Ramucirumab PK samples will be collected at SOI at Cycle 7 only.

c tusamitamab rfvntansine PK samples will be collected at SOI each cycle at Cycles 5, 6 and 7 and thereafter at Cycle 13 only.

d tusamitamab rfvntansine ATA samples will be collected at SOI at Cycle 7 and thereafter every 6 cycles (ie, C7, C13, C19...).

Note: The sampling time-points for PK and ATA may be reduced during the course of the study based on the updated knowledge of drug behavior, upon notification from the Sponsor.

1.3.3.3 Triplet cohort

Cycle		C1	C2	C3	C4	C6	C8	C13	C18 then every 5 cycles (C23, ...)	EOT
Day		D1	D30 ±5 days after last IMP							
Tusamitamab ravtansine	IV infusion	X	X	X	X	X	X	X	X	
	Sample RNT (hours) Ref. tusamitamab ravtansine SOI	SOI	SOI	SOI	SOI	SOI	SOI	SOI	SOI	
	Sample time window	(-24 h, SOI)								
	PK sample ID	P00 ^a								
	ATA sample ID	AB00 ^a	ABF00							

Note: The sampling time-points for PK and ATA may be reduced during the course of the study based on the updated knowledge of drug behavior, upon notification from the Sponsor.

^a Samples collected strictly before start of infusion (SOI).

ATA: anti-therapeutic antibody; C: Cycle; D: Day; EOT: end of treatment; h: hour; IMP: investigational medicinal product; IV: intravenous; P: plasma; PK: pharmacokinetics; RNT: relative nominal time; SOI: start of infusion.

2 INTRODUCTION

Despite recent progress in the treatment of advanced NSCLC, there remains a need for effective new treatment at the time of disease progression. Current therapeutic approaches combining an inhibitor of angiogenesis in combination with a systemic cytotoxic agent such as docetaxel entail serious hematological and other toxicities; therefore, targeted cytotoxic therapies may offer an improvement in safety and tolerability as well as efficacy.

One feature that can be used to target some tumor cells is surface expression of carcinoembryonic antigen-related cell adhesion molecule 5 (CEACAM5), first described in 1965 as a tumor-associated antigen in human colon cancer tissue extracts (3). High levels of CEACAM5 expression have since been observed in several epithelial tumors, whereas in normal adult tissue, its expression is limited to few tissues (4, 5). Immunostaining of CEACAM5 in a large panel of human tumor tissue microarray samples has shown the highest prevalence of cell surface CEACAM5 expression in adenocarcinomas of the colon and of the stomach and its subtypes as well as NSQ NSCLC.

Maytansinoids are antimitotic agents that inhibit microtubule formation to act as very potent cytotoxic agents against tumor cell lines in vitro, with IC₅₀ values 100- to 1000-fold more potent than conventional tubulin binding compounds, including docetaxel. Tusamitamab ravtansine is an antibody to CEACAM5 conjugated to the cytotoxic maytansinoid agent, (DM4). Encouraging preliminary antitumor activity of tusamitamab ravtansine in patients heavily pretreated for NSQ NSCLC has been demonstrated in an ongoing study (TED13751).

2.1 STUDY RATIONALE

Tusamitamab ravtansine is an antibody-drug conjugate (ADC) combining hu769_4D4 (SAR408377), a humanized antibody that recognizes selectively the A3-B3 extracellular domain of CEACAM5 with the potent cytotoxic maytansinoid derivative, DM4, an inhibitor of microtubule assembly. tusamitamab ravtansine is expected to selectively deliver DM4 to cancer cells expressing the CEACAM5 antigen, such as colon, stomach and its signet-ring cell subtype as well as NSQ NSCLC.

In the first-in-human monotherapy study (TED13751), the maximum tolerated dosage of tusamitamab ravtansine was identified to be 100 mg/m² every 2 weeks. Dose-limiting toxicities were mainly Grade 3 microcystic keratopathy; all were reversible. This dose is also the selected started dose for combination studies.

In the expansion phase of study TED13751, a cohort of patients with heavily pretreated NSQ NSCLC tumors testing positive for CEACAM5 ($\geq 2+$ in intensity on membranes of $\geq 50\%$ of the tumor cells) have been treated with tusamitamab ravtansine at 100 mg/m² every 2 weeks. Results from the 64 evaluable patients showed encouraging antitumor activity associated with a response rate of 20.3% (95% CI, 12.3% to 31.7%) (6).

Ramucirumab (Cyramza®); a human IgG1 monoclonal antibody that inhibits VEGFR-2 is approved in combination with docetaxel for the treatment of patients with metastatic NSCLC.

This approval was based on the results of a Phase 3 study (REVEL) a randomized placebo-controlled trial of 1,253 patients with metastatic NSCLC previously treated with a platinum-based combination therapy. Patients were randomized to receive either ramucirumab in combination with docetaxel or placebo in combination with docetaxel. The primary endpoint was overall survival (OS). Patients who received ramucirumab in combination with docetaxel had improved OS (hazard ratio: 0.86; 95% CI, 0.75 to 0.98). Median OS was 10.5 months on the ramucirumab plus docetaxel arm versus 9.1 months on the placebo plus docetaxel arm. Median progression free survival was 4.5 months for the ramucirumab arm compared to 3 months in the control arm (hazard ratio: 0.76; 95% CI, 0.68 to 0.86). Objective response rate was 22.9% for the ramucirumab arm (95% CI, 19.7% to 26.4%) compared to 13.6% in the control arm (7).

Ramucirumab 10 mg/kg Q3W in combination with docetaxel is approved to treat metastatic NSCLC. Additionally, ramucirumab 8 mg/kg administered Q2W is approved to treat other advanced cancers: as a single agent or in combination with paclitaxel for gastric or gastro-esophageal junction adenocarcinoma, and in combination with a FOLFIRI regimen for CRC. The dosing schedule selected for this study is supported by efficacy data from studies with tusamitamab ravtansine 100 mg/m² Q2W (see Investigator's Brochure for tusamitamab ravtansine) and the Q2W dosing schedule for ramucirumab approved for other cancer indications (see Cyramza® prescribing information).

Combined ICI and VEGF/VEGF receptor inhibition have shown benefit in multiple tumor types through immune modulation. Pembrolizumab and ramucirumab (P+R) were evaluated in patients with advanced, ICI-exposed, in a substudy of Lung-MAP1, a master protocol for patients with Stage IV previously treated NSCLC. In this randomized, Phase II study from the Lung-MAP platform, 136 patients were randomized to receive pembrolizumab + ramucirumab or the Investigator's choice of standard therapeutic regimens (SOC). Ramucirumab 10 mg/kg and pembrolizumab 200 mg Q3W were used. Overall survival (OS) was significantly improved with P+R compared to SOC: median (95% CI) OS was 14.5 (13.9 to 16.1) months for P+R; and 11.6 (9.9 to 13.0) months for SOC (HR: 0.69 [0.51 to 0.92], P value from the standard log-rank test equal to 0.05 and 0.15 from the weighted log-rank test). Neither progression-free survival (PFS) or objective response rate (ORR) differed between the treatment arms (2).

Addition of pembrolizumab could be a new option for the treatment of advanced NSQ NSCLC after platinum and ICI. A new cohort of 6 to 12 patients will be added to this protocol in order to assess the safety of this tri-therapy (tusamitamab ravtansine-ramucirumab-pembrolizumab) and validate the dose of tusamitamab ravtansine to be used in case of further development of this combination in this indication.

The balance of anticipated benefits and the reported risks of tusamitamab ravtansine identified in ongoing studies TED13751 and TCD15054 supports its continued clinical development, both as monotherapy and in combination regimens with chemotherapy and immunotherapy agents. Given the considerable risks of adverse effects including neutropenia, anemia, and infection associated with docetaxel, the combination of tusamitamab ravtansine with ramucirumab may represent a treatment regimen with an improved safety profile as compared to the approved combination of docetaxel and ramucirumab.

The combination of tusamitamab ravtansine with ramucirumab with or without pembrolizumab will provide efficacy and safety data in patients with CEACAM5-positive (CEACAM5 $\geq 50\%$) NSQ NSCLC tumors.

